9.3. Prior and Concomitant Medication

Medications will be presented for the safety analysis population and coded using WHODRUG V2014Q1 or higher. Preferred Anatomic Therapeutic Chemical (ATC) coding will be applied. Medications will be presented by ATC Level 1, ATC Level 4.

‘Prior’ medications are medications which started and stopped prior to the flortaucipir injection. ‘Concomitant’ medications are medications that started prior to, on or after the flortaucipir injection *and* ended on or after the date of the flortaucipir injection or were ongoing at the end of the study.

Prior and concomitant medications will be presented in a listing including:

- Preferred term
- Indication
- Total daily dose
- Dose unit
- Frequency
- Route
- Start date
- End date
- Ongoing (Y/N)
- Used for AE (Y/N)

For table summaries, the ATC Level 1s will be sorted by descending frequency of the total number of subjects with at least one medication. Within each ATC Level 1, the ATC Level 4s will be sorted by descending frequency of the total number of patients with at least one medication in each category.

9.3.1. Missing and Partially Missing Start and Stop Dates

See appendix 1.1 for specific algorithms to impute missing start and stop dates.

9.4. Electrocardiogram & Routine Laboratory Data

A resting 12-lead ECG and clinical laboratory evaluations will be performed at screening.

Safety labs performed at screening will include hematology, chemistry and urinalysis including plasma thiamine (vitamin B1) level.

This ECG and laboratory data will be summarized in listing with the following information for the safety analysis population:

- Collected at Screening (Y/N)

- Collection Date
- Collection Time

9.5. MRI

If a volumetric MRI has not been performed as part of PFBHS within six months days of the flortaucipir PET imaging visit, a volumetric MRI is to be performed as part of this study's screening assessments.

MRI data will be summarized in a listing and table for the following regions (normalized to intracranial volume)

- Whole Brain Volume
- Total Gray Volume
- Hippocampal Volume
- Ventricle Volume

9.5.1. Missing and Partially Missing Start and Stop Dates

See appendix 1.1 for specific algorithms to impute missing start and stop dates.

9.6. Baseline Vital Signs

Baseline vital signs will be presented in a listing, and will include:

- Pulse rate (bpm)
- Respiratory rate (breaths/minute)
- Supine blood pressure (mmHg)
- Height (cm)
- Weight (kg)

9.6.1. Imputation for Missing Scale Items

No imputation method will be used for missing baseline vital sign data.

10. EFFICACY ANALYSIS

10.1. Primary Efficacy Analysis

10.1.1. Efficacy Variable

The relationship of flortaucipir uptake will be evaluated both quantitatively (SUVr) and qualitatively using assessments from a visual read of the signals from images, classifying scans as ‘No uptake’, ‘Mild uptake’, ‘Moderate uptake’, and ‘Intense uptake’.

The flortaucipir PET SUVr will be generated as an average SUVr across selected AAL defined regions and a weighted average (MUBADA) SUVr based on regions used in other studies to discriminate among AD and control groups.

Efficacy analyses will be conducted separately on these two sets of SUVr and the qualitative read.

10.1.2. Hypothesis Tests

There are no formal hypothesis testing planned for this study. All the statistical hypothesis testing described below are for exploratory purpose only.

10.1.2.1. Hypothesis #1: Difference in Quantitative Flortaucipir Uptake Between Cognitive Groups

The mean flortaucipir SUVr difference between cognitive statuses (cognitively impaired vs without cognitive or behavioural complaint) will be tested with the following hypothesis.

$$H_0 : \mu_{CI} = \mu_{CN}$$

$$H_A : \mu_{CI} \neq \mu_{CN} ,$$

Where:

- μ_{CI} is the mean flortaucipir SUVr in the cognitively impaired group
- μ_{CN} is the mean flortaucipir SUVr in the cognitive normal group

10.1.2.2. Hypothesis #2: Difference in Quantitative Flortaucipir Uptake Between Fighter Groups

The mean flortaucipir SUVr difference between fighting groups (active vs retired) will be tested with the following hypothesis.

$$H_0 : \mu_{Act} = \mu_{Ret}$$

$$H_A : \mu_{Act} \neq \mu_{Ret} ,$$

Where:

- μ_{Act} is the mean flortaucipir SUVr in the active fighters
- μ_{Ret} is the mean flortaucipir SUVr in retired fighters

10.1.2.3. Hypothesis #3: Association of Qualitative Flortaucipir Uptake and Cognition

The association of flortaucipir uptake ('No uptake', 'Mild uptake', 'Moderate uptake', 'Intense uptake') and cognitive status ('Cognitively Impaired', 'Cognitive Normal') will be tested with the following hypothesis.

H₀: Cognitive status and qualitative flortaucipir uptake are independent

H_A: Cognitive status and qualitative flortaucipir uptake are not independent

10.1.2.4. Hypothesis #4: Association of Qualitative Flortaucipir Uptake and Fighter Status

The association of flortaucipir uptake ('No uptake', 'Mild uptake', 'Moderate uptake', 'Intense uptake') and fighter status ('Retired', 'Active') will be tested with the following hypothesis.

H₀: Fighter status and qualitative flortaucipir uptake are independent

H_A: Fighter status and qualitative flortaucipir uptake are not independent

10.1.3. Primary Analysis

Descriptive statistics for flortaucipir SUVr will be reported overall and by each enrolment group. Box-and-whisker plots of flortaucipir SUVr will be created to visually display tau distribution across these groups.

Hypotheses 1 and 2 will be tested using a two-way ANOVA, with fighters status (active or retired) and cognitive status (impaired or normal) as two main factors. The comparisons of mean SUVr values will be compared through setting up proper contrasts.

The descriptive statistics and ANOVA analysis will be summarized in a table and include the following:

- n
- Mean (SD)
- Median
- Min, Max
- Overall P-value from ANOVA
- P-values from each contrast

Hypotheses 3 and 4 will be tested using Fisher's exact test. The distributions for each enrollment group will be presented in a 4x2 contingency table along with the p-values from each test.

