Protocol Number: ^{18}F -AV-1451-A11

^{18}F -AV-1451 PET Imaging in Professional Fighters

Date and Version:

13 July 2015, Amendment 1

[figure not shown]
Name of Compound:

^{18}F -AV-1451 ([F-18]T807)

Sponsor:

Avid Radiopharmaceuticals
Philadelphia, Pennsylvania USA

Approvals/Signatures and Date:

CONFIDENTIAL

This material is the property of Avid Radiopharmaceuticals (Avid). The information is confidential and is to be used only in connection with matters authorized by Avid and no part of it is to be disclosed to others without prior written permission from Avid.

Sponsor: Avid Radiopharmaceuticals	Name of Compound: ¹⁸ F-AV-1451([F-18]T807)	Active Ingredient(s): 7-(6-[F-18]fluoropyridin-3-yl)-5H-pyrido[4,3-b]indole
Title of Study: ¹⁸ F-AV-1451-A11 “ ¹⁸ F-AV-1451 PET Imaging in Professional Fighters”		
Planned number of subjects (Enrolled): Approximately 30 This study will be divided into the following groups: 
 1. Approximately 15 active professional fighters (boxers and mixed martial artists) who have had at minimum 10 professional fights. 
 a. Approximately 10 with cognitive impairment b. Approximately 5 without cognitive or behavioral complaints 2. Approximately 15 retired professional fighters (boxers and mixed martial artists). 
 a. Approximately 10 with cognitive impairment b. Approximately 5 without cognitive or behavioral complaints Subjects will be recruited from the pool of participants in the Professional Fighters Brain Health Study (PFBHS).		
Name of compound: ¹⁸ F-AV-1451([F-18]T807) Dose: 370 MBq (10 mCi) Route of Administration: Intravenous (IV) bolus		
Study Phase: I		
Study Centers: 1-3 centers in the United States		
Trial Objectives: The primary objectives of this study are: 
 • To explore the use of ¹⁸F-AV-1451 as a biomarker for brain injury related to repetitive head trauma; and • To examine the relationship between clinical presentation and tau deposition as measured by ¹⁸F-AV-1451 uptake in active and retired professional fighters. A secondary objective of this study is: 
 • To expand the ¹⁸F-AV-1451 safety database. 		
Eligibility: Only subjects duly consented and enrolled in the PFBHS protocol (conducted by the Cleveland Clinic with [name] as Principal Investigator) will be considered for participation in this study (see Section 5.3, Selection of Subjects).		

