2. STUDY OBJECTIVES

2.1. Primary Objective

The primary objectives of this study are:

- To explore the use of flortaucipir as a biomarker for brain injury related to repetitive head trauma; and
- To examine the relationship between clinical presentation and tau deposition as measure by flortaucipir uptake in active and retired professional fighters.

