10.1.4. Exploratory Analysis

A correlation analysis will be performed to investigate the relationship between flortaucipir SUVR and:

- MMSE
- Beck Depression Inventory II
- Digit span forward/backward
- MRI brain volumes (normalized to intracranial volume)
 - Whole brain volume
 - Gray volume
 - Hippocampal volume
 - Ventricle volume

Contingent on a trending significance in the primary analysis ($p \leq 0.1500$ for contrasts), more correlation analysis will be performed to investigate the relationship between tau deposition as measured by flortaucipir SUVR and:

- Years of fighting
- Age when fighting began
- Number of bouts
- Number of losses
- Number of wins
- Number of draws
- Number of knockouts

A multivariate model may also be derived assuming strong relationships found in the primary and correlation analyses.

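### The graded visual read gets only a 4x2 table and Fisher's exact test; adding one effect estimate with a confidence interval and an exact test of shift would be a cheap, low-impact improvement

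*SAP*

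**What the plan says.** SAP 10.1.1 sets up three flortaucipir outcomes, two SUVr measures and a four-grade visual read, and adds: "Efficacy analyses will be conducted separately on these two sets of SUVr and the qualitative read".

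For the read, the alternatives in SAP 10.1.2.3 and 10.1.2.4 are general: "Cognitive status and qualitative flortaucipir uptake are not independent" and "Fighter status and qualitative flortaucipir uptake are not independent". SAP 10.1.3 then states "Hypotheses 3 and 4 will be tested using Fisher's exact test" and describes the output: "The distributions for each enrollment group will be presented in a 4x2 contingency table along with the p-values from each test". The template code in Appendix II (1.1.3 and 1.1.4) requests the Fisher option and nothing else. SAP 6.1 adds counts and percentages for discrete variables. The correlations in SAP 10.1.4 use SUVr, not the read.

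All testing is exploratory (SAP 10.1.2), at 0.05 without multiplicity correction (SAP 10.1.3.1), and no sample size was calculated (SAP 3.2).

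**The concern.** The four grades run from none to intense. The documents do not call the scale ordered, but the labels leave little doubt. Fisher's test treats the grades as unrelated categories: shuffling them leaves its p-value unchanged. If one group's reads are shifted upward, that information is not used.

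The second primary objective is "To examine the relationship between clinical presentation and tau deposition as measure by flortaucipir uptake in active and retired professional fighters". For the read, a reader will see percentages by group and a p-value, but no single estimate of how far the groups differ and no statement of its uncertainty. With about 30 subjects, that estimate and its interval say more than a p-value.

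**Working it through.** The plan states no power or effect size for the read, so there is no figure to reproduce.

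**Inputs from the documents.** The Protocol synopsis lists "Approximately 10 with cognitive impairment" and approximately 5 without complaints, in both the active and the retired group. That gives 10 + 10 = 20 impaired against 5 + 5 = 10 normal for Hypothesis 3, and 15 against 15 for Hypothesis 4. Alpha is 0.05 (SAP 10.1.3.1).

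**Assumed inputs.** Reference-group reads (none/mild/moderate/intense, %): 60/25/10/5, 40/30/20/10, 80/12/5/3, 90/7/2/1 and an even 25 each. For a proportional-odds shift, each cumulative odds c/(1 − c) in the reference group is divided by the odds ratio (OR). At 20 vs 10 the group of 20 is the shifted one.

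**Method.** Every possible table was enumerated: 1,771 × 286 = 506,506 at 20 vs 10, and 816 × 816 = 665,856 at 15 vs 15. Each received its exact Fisher p-value and its exact two-sided Wilcoxon p-value (midranks), weighted by its multinomial probability.

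**Illustration (invented counts).** Impaired 6/6/5/3, normal 7/2/1/0.
- Fisher p = 0.268; exact Wilcoxon p = 0.034. One reordering of the grades leaves Fisher at 0.268 and moves Wilcoxon to 0.091.
- Share of normals below each grade, ties counted one half: 0.35, 0.80, 0.95, 1.00.
- Probability of a higher read = (6×0.35 + 6×0.80 + 5×0.95 + 3×1.00)/20 = 14.65/20 = 0.7325.
- DeLong standard error = √(0.0714/20 + 0.0414/10) = 0.0878, where 0.0714 and 0.0414 are the variances of these shares in the impaired and of their counterparts (0.85, 0.55, 0.275) in the normals.
- Logit scale: ln(0.7325/0.2675) = 1.007; 0.0878/(0.7325×0.2675) = 0.448; 1.007 ± 1.96×0.448 gives 0.129 and 1.886, hence a 95% CI of 0.53 to 0.87.

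**Power.** With the 60% base and OR 4, Fisher has 24.0% and exact Wilcoxon 43.8% at 20 vs 10; the figures at 15 vs 15 are 33.9% and 48.7%. The largest gain is with the 80% base and OR 8 at 20 vs 10: 45.4% against 70.6%.

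| Assumed difference | Wilcoxon minus Fisher, points |
|---|---|
| OR 4 to 8; 40, 60 or 80% base | +10.7 to +25.2 |
| OR 3; same bases | +6.1 to +14.3 |
| OR 2; same bases | +1.3 to +6.2 |
| OR 4 / OR 8; even base, 20 vs 10 | +8.4 / +6.8 |
| OR 2; 90% base | −0.3 to +0.2 |
| OR 4; 90% base | +1.7 to +6.9 |
| 20–40% of one group moved to moderate and intense, half each; 40, 60 or 80% base | +1.9 to +13.3 |
| 20–40% of one group moved entirely to intense; 40, 60 or 80% base | 0.0 to −12.3 |

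The last row is not general either. With the even base at 15 vs 15, Wilcoxon is ahead by 0.9 to 4.8 points.

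**A non-monotone case.** Take .60/.05/.05/.30 against .60/.30/.10/0. Fisher has 63.0% (20 vs 10) and 71.1% (15 vs 15), Wilcoxon 6.4% and 10.1%. The probability of a higher read is .60×.30 + .05×.75 + .05×.95 + .30×1.00 = 0.565, although intense uptake is 30% against 0%.

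**Type I error if either test counts.** 6.1–7.4% with the 60 and 40% bases, about 7.5% with the even base, 3.5–4.3% with 80% and 0.7–1.8% with 90%.

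**Interval.** Over 96 settings (2 sizes × 4 bases, without the even one, × 12 alternatives), the logit-scale DeLong interval covers 92.4–97.5%, with mean half-width 0.105–0.198. It is undefined in up to 4.2% of trials (90% base, no effect) and in at most 1.0% otherwise. With the 60 and 40% bases it covers 94.8–96.2%, against 89.9–93.8% for an untransformed Wald interval and 89.7–94.5% for a percentile bootstrap (bootstrap simulated in 48 of the settings).

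**The case against.** The strongest case against is that nothing is wrong. Fisher's test matches the written alternatives, all testing is exploratory, and neither test is better in general. That stands, and it is why this is an optional addition and not a correction.

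Three stronger readings are tempting, and the documents do not support them.
- *Fisher is the wrong test and should be replaced.* It is valid for general association, and it is far ahead in the non-monotone case above.
- *The plan gives no number for direction or size.* SAP 6.1 and 10.1.3 give counts and percentages by group, which show both. Only a one-number summary and its interval are missing.
- *The Fisher p-value steers later modelling.* SAP 10.1.4 says "A multivariate model may also be derived assuming strong relationships found in the primary and correlation analyses", but leaves strength undefined. The one numerical trigger in that section refers to contrasts, which exist only for SUVr. Nothing ties the model to the visual read.

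Three further objections stand in part. The SUVr contrasts have no planned CI either, so this is a general reporting habit; that does not weaken the case for the read. The two p-values will sometimes disagree at 0.05: under OR 4 to 8 with the 40, 60 and 80% bases, in roughly 16% to just over a quarter of trials. The added test also has no hypothesis of its own in SAP 10.1.2. The text must therefore say which question each test answers.

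**Conclusion.** The point holds as a cheap improvement of low impact. That no summary effect with a CI and no order-using analysis is planned for the read follows from the SAP alone, apart from inferring the order from the labels. The power gain of about 11 to 25 points rests on the assumed read rates, a proportional-odds shift of OR 4 to 8 and the planned, approximate group sizes. It is smaller for weaker shifts, and for evenly spread reads at 20 vs 10. It vanishes at OR 2 when nearly all reads are negative, and can reverse when the difference is intense-only or non-monotone. Adding the ordered test is supported; demoting Fisher is not.

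**What to change.** Keep SAP 10.1.2.3, 10.1.2.4, Fisher's exact test and the 4x2 table as written. Add to SAP 10.1.3:

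- The probability of a higher read (ties counted one half; impaired over normal, retired over active), with a 95% CI from the DeLong standard error on the logit scale. If the standard error is 0, or the estimate is 0 or 1, report the estimate only.
- A supplementary exact two-sided Wilcoxon rank-sum test on the read coded 0 to 3 with midranks.
- A statement that Fisher addresses any association and Wilcoxon a shift, that both p-values are shown, and that significance on either alone is not claimed as one result.
- A statement that the summary is read beside the 4x2 table, because it can lie near 0.5 when groups differ non-monotonically.

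In Appendix II, keep PROC FREQ. For each factor, add PROC NPAR1WAY with EXACT WILCOXON, PROC LOGISTIC with an ROC statement to obtain the area and its standard error, and a DATA step for the logit limits. Name the event level for both factors (impaired for COGGRP, retired for FIGHTGRP) using the stored data values. In the template, CI appears only in a contrast label, and modelling the wrong level would reverse the estimate.

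The cost is one paragraph and about ten lines of code, with no new data. The downside is one extra uncorrected exploratory p-value per hypothesis.

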10.1.3.1. Statistical Considerations in Primary Analysis

All hypothesis testing will be run at the 0.05 level of significance. Because this is a Phase I study, no correction for multiplicity will be applied to control for alpha.

10.1.4. Exploratory Analysis

A correlation analysis will be performed to investigate the relationship between flortaucipir SUVR and:

- MMSE
- Beck Depression Inventory II
- Digit span forward/backward
- MRI brain volumes (normalized to intracranial volume)
 - Whole brain volume
 - Gray volume
 - Hippocampal volume
 - Ventricle volume

Contingent on a trending significance in the primary analysis ($p \leq 0.1500$ for contrasts), more correlation analysis will be performed to investigate the relationship between tau deposition as measured by flortaucipir SUVR and:

- Years of fighting
- Age when fighting began
- Number of bouts
- Number of losses
- Number of wins
- Number of draws
- Number of knockouts

A multivariate model may also be derived assuming strong relationships found in the primary and correlation analyses.

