The Professional Fighters Brain Health Study (PFBHS) being conducted at the Cleveland Clinic Lou Ruvo Center for Brain Health is a longitudinal study that focuses on a sample of active and retired professional fighters, and compares them with a control cohort matched for age and level of education. The primary objective of the PFBHS is to determine the relationship between measures of head trauma exposure and other potential modifiers and changes in brain imaging, neurological and behavioral function over time (Bernick, 2013). In this context, the addition of an imaging biomarker that could identify the presence of underlying tau pathology might be useful in understanding the etiology and evolution of CTE, and could potentially identify cases at risk for subsequent neurodegeneration or other clinically important outcomes with implications for management of CTE and/or TBI cases.

¹⁸F-AV-1451 (originally named [F-18]T807 by Siemens Molecular Imaging Biomarker Research group) has been developed as a positron emitting radiopharmaceutical for *in vivo* imaging of tau protein aggregates (Xia et al., 2013). Autoradiography results using tissue sections from human brains showed a strong signal in the grey matter of cortical slices from tau positive brains, but weak or no binding in tau negative, A β positive, or tau and A β negative tissue. Scatchard analysis based on this heterogeneous autoradiography assay yielded an estimated K_d of 15nM. A saturation binding experiment using purified PHF tau isolated from brains of AD patients yielded a K_d value of 0.54 nM.

AV-1451 was assessed in competitive binding assays against a panel of 72 of the most common central nervous system (CNS) targets and no clinically relevant inhibition was seen. AV-1451 was positive in the *in vitro* hERG assay; however, *in vivo* cardiovascular safety pharmacology assessments in dogs showed no evidence of QT prolongation at doses up to 50x the intended maximum human dose (MHD). Nonetheless, until sufficient human cardiovascular safety data are available, initial clinical studies will exclude subjects with a history of risk factors for Torsades de Pointes and subjects taking drugs known to prolong the QT interval.

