7. PROCEDURES AND METHODS

7.1 Assessment Periods (See Section 11.2, Trial Flow Chart)

The study will consist of the following sequence of activities:

7.1.1 Screening Visit:

Subjects currently enrolled in the PFBH study protocol will be contacted to participate. Screening assessments may take place over several days, within 90 days of the ^{18}F -AV-1451 PET scan, and will include:

- Informed Consent will take place before any ^{18}F -AV-1451-A11 study procedures;
- Demographics (birth year, gender, race, ethnicity, education, alcohol, drug use and smoking);
- Medical history and concomitant medications;
- Safety assessments: Vital signs (pulse rate, respiratory rate, supine blood pressure, height and weight), ECG (with results reviewed prior to ^{18}F -AV-1451 administration), and safety labs (hematology, chemistry and urinalysis) including plasma thiamine (vitamin B1) level;
- Mini-Mental State Examination (MMSE);
- Digit span forward and backward;
- Beck Depression Inventory II;
- If a volumetric MRI has not been performed as part of PFBHS within six months of the ^{18}F -AV-1451 PET imaging visit, a volumetric MRI is to be performed as part of this study’s screening assessments; and
- A physician will see the subject during the screening assessments.

7.1.2 *Imaging Visit(s)*

^{18}F -AV-1451 PET Imaging Visit

- A physician or a licensed/credentialed medical professional (i.e., a PET technologist, imaging center nurse or a regional equivalent) designated by the site principal investigator must assess or evaluate the subject prior to administration of ^{18}F -AV-1451 Injection to determine if they are still suitable to undergo the scan. If a designee performs this activity, a physician must be available to provide medical consultation;
- Vital signs will be taken (pulse rate, respiratory rate, supine blood pressure) at the following time points:
 - Prior to administration of ^{18}F -AV-1451 Injection (Weight will also be collected)
 - Within 5 minutes after completion of injection of ^{18}F - AV-1451 Injection
 - After completion of the PET scan prior to discharge;
- Subjects will receive a single IV bolus injection target dose of 370 MBq (10 mCi) of ^{18}F -AV-1451 Injection followed by a saline flush.
- At approximately 75 minutes following injection, a continuous 30-minute brain scan will begin;
- The injection site will be observed for excessive inflammation or damage to the surrounding tissue where the dose was injected;

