9. BASELINE PATIENT DATA

9.1. Baseline Demographics and Characteristics

Demographic data and other baseline characteristics will be presented for the flortaucipir safety analysis population in a table.

The most recent value prior to a subject's initial injection of flortaucipir will be considered the baseline value, and will be reported in the demographics table. The following data from the will be reported in the baseline and demographics table:

- Age (years)
- Gender
- Race
- Ethnicity
- Highest Level of Education
- Alcohol use
- Tobacco use
- Recreational Drug Use
- Height (cm)
- Weight (kg)
- MMSE
- Beck Depression Inventory II
- Digit span forward/backward

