10.1.4.1. Subgroup Analysis

All correlation analysis conducted will be performed for each cognitive group separately, and results will be provided in a table.

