1.1.4. HYPOTHESIS #4

```
PROC FREQ data = <data>;
table VISREAD*FIGHTGRP / fisher;
RUN;
```

1.2.SAMPLE CODE FOR EXPLORATORY ENDPOINT

```
ods output PearsonCorr=corr;  
PROC CORR data = <data> pearsons;  
var <variable list>;  
RUN;
```

1.3.SAMPLE CODE FOR TEAE TABLES BY DESCENDING FREQUENCY

```
ods output crosstabfreqs=xtab;  
PROC FREQ data = <data> order=freq;  
table <SOC variable>*<Preferred Term variable>;  
RUN;
```

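### The planned correlations of uptake with MMSE and digit span make no allowance for education, which is collected; depending on how education relates to the scores and to uptake, this can cost power or produce a false relation

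*SAP*

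**What the plan says.** SAP 10.1.4 plans the analysis in these words: "A correlation analysis will be performed to investigate the relationship between flortaucipir SUVR and" MMSE, Beck Depression Inventory II, digit span and four MRI volumes. No covariate is named. The template in SAP Appendix II, 1.2 is "PROC CORR data = <data> pearsons", with no PARTIAL statement. SAP 10.1.4.1 adds: "All correlation analysis conducted will be performed for each cognitive group separately, and results will be provided in a table".

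The screening list in Protocol 7.1.1 includes "Demographics (birth year, gender, race, ethnicity, education, alcohol, drug use and smoking". The only use the SAP makes of education is one row, "Highest Level of Education", in the baseline table of SAP 9.1.

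The one possible route to adjustment is the last sentence of SAP 10.1.4: "A multivariate model may also be derived assuming strong relationships found in the primary and correlation analyses". SAP 10.1.2 labels all testing exploratory, and SAP 3.2 says there was no sample size calculation.

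**The concern.** The second primary objective is to relate clinical presentation to tau uptake. MMSE and digit span are objective cognitive measures obtained in this study, and apart from the optional multivariate model these correlations are the only planned analysis that uses them as continuous scores.

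Two separate things can go wrong, under different conditions. If the scores vary with schooling but uptake does not, schooling is noise: the unadjusted r is diluted and power falls, while the type I error stays at 5%. If schooling is related to both, the unadjusted r is not zero even when uptake and cognition are unrelated at a given level of schooling. With less schooling going with higher uptake and lower scores, the false r is negative, which is the direction that would be read as a tau effect.

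**Working it through.** **Inputs from the documents.** About 30 subjects: 10 + 5 active and 10 + 5 retired, so about 20 impaired and 10 unimpaired (Protocol synopsis). Level 0.05 with no multiplicity correction (SAP 10.1.3.1). Sidedness is not stated for the correlations; two-sided is assumed. The plan gives no power or effect size, so there is no figure to reproduce.

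**Assumptions.** Unadjusted correlation 0.4; share s of score variance explained by education, from 0 to 30%; correlation a between education and uptake. None of these is in the documents.

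**Power when education is unrelated to uptake (a = 0).** The partial correlation is r_p = r / √(1 - s). With s = 0.20, r_p = 0.4 / √0.80 = 0.447. Approximate power is Φ(atanh(r)·√(n - 3 - k) - 1.96), with k = 0 unadjusted and k = 1 adjusted for one education term. At n = 30:

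- unadjusted: 0.4236 × √27 - 1.96 = 0.241, power 59.5%
- adjusted, s = 0.20: 0.481 × √26 - 1.96 = 0.494, power 68.9%

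Simulating the t tests themselves (n - 2 and n - 3 degrees of freedom) gives values one to two points higher. The table shows simulated power, unadjusted / adjusted, in %:

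| Education share s | r_p | n = 30 | n = 20 | n = 10 |
|---|---|---|---|---|
| 0 | 0.400 | 61 / 59 | 43 / 41 | 21 / 19 |
| 5% | 0.410 | 61 / 62 | 43 / 43 | 21 / 20 |
| 10% | 0.422 | 61 / 65 | 43 / 45 | 21 / 21 |
| 20% | 0.447 | 61 / 71 | 43 / 50 | 21 / 23 |
| 30% | 0.478 | 61 / 77 | 43 / 57 | 21 / 26 |

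Holding the partial correlation fixed instead gives the same picture. With r_p = 0.5 and n = 30, adjusted power is 80.0%, against 79.5, 76.9, 73.0 and 67.3% unadjusted when education correlates 0.2, 0.3, 0.4 and 0.5 with the score (shares of 4, 9, 16 and 25%).

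**False relation.** If the partial correlation is zero, the unadjusted correlation is a·√s. With a = -0.3 and s = 0.20 it is -0.3 × 0.447 = -0.134. The rejection rate is Φ(d - 1.96) + Φ(-d - 1.96) with d = 0.135 × √(n - 3):

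- n = 30: d = 0.70, rate 10.8% (about 11% simulated)
- n = 20: d = 0.56, rate 8.6%
- n = 10: d = 0.36, rate 6.5% (about 6% simulated)

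With a = -0.4 and s = 0.25 the false r is -0.20 and the rate at n = 30 is about 18%. With a = 0 it is 5% for any s. The adjusted test stays at about 5% in every case.

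**Both relations present and a true effect.** Power can then move either way. With r_p = -0.5, n = 30 and both education correlations +0.3, the unadjusted r is -0.5 × 0.91 + 0.09 = -0.365, and power is 52% against 81% adjusted. With opposite signs it is -0.5 × 0.91 - 0.09 = -0.545, and 90% against 81%. The extra power in the second case comes from confounding.

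**The case against.** The strongest reply is that the benefit rests on relations the documents do not contain. Protocol 7.2 describes MMSE and digit span without mentioning schooling, and nothing links schooling to fight history or uptake. Every test is exploratory, there is no power target to miss, and zero-order correlations are a normal first description in a phase I study of about 30. This stands, and it is why the point is conditional and minor.

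SAP 10.1.4.1 also has the correlations run within groups of about 20 and 10, where the gain shrinks or reverses. That stands too, as the table shows.

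The cost of adjusting can exceed one degree of freedom. The SAP variable reads as a category. If it had five levels entered as indicators (an assumption; 4 degrees of freedom), adjusted power at a 20% share would be 65% at n = 30, 42% at n = 20 and 14% at n = 10, so most of the gain is lost and the smallest group is worse off. The fix therefore has to say how education is coded.

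The optional multivariate model does not answer the point. It is considered only after strong relations have been found, lists no covariates, and cannot recover a relation hidden by noise in the scores.

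A reader might infer from the Protocol Introduction, where the parent study "compares them with a control cohort matched for age and level of education", that the sponsor regards education as something to be held fixed in this analysis. The documents do not support that. The matching is between fighters and controls, this study has no controls, and matching across cohorts says nothing about the spread of education among fighters or its link to uptake. The same sentence names age as well.

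**Conclusion.** The omission is real: education is collected, and no planned analysis of SUVr against the cognitive scores uses it. The consequences are conditional. At n = 30 and an assumed r of 0.4, adjustment gains about 4 points of power if education explains 10% of score variance and about 10 points at 20%, and loses under 2 if it explains nothing. A false relation needs education to be related to uptake as well; at -0.3 with a 20% share the error rate is about 11% in the full group, 8.6% at n = 20 and 6% at n = 10.

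Two stronger readings are tempting: that the plan does lose power, and that its correlations will be confounded. Neither follows, because the documents give no relation of education to scores or uptake among these fighters. What holds is that a variable already in hand can guard against both risks at small cost in the full group. In the subgroups the case is weak, and in the group of about 10 adjustment can cost about 2 points.

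**What to change.** In SAP 10.1.4, for MMSE and digit span forward and backward, report beside the planned unadjusted r a partial correlation (or regression slope) with 95% CI, adjusted for education entered as a single numeric term. State in the SAP whether that term is years or an ordered level score. Add the matching PARTIAL statement to the template in Appendix II, 1.2.

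Name the adjusted result as the main one for the full group of about 30. Say that in the cognitive groups of about 20 and 10 it is to be read cautiously, since adjustment may gain little or cost about 2 points of power. Keep the exploratory label.

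The cost is a sentence or two in the SAP, one line of code, a rule for scoring education and one degree of freedom. No new data are needed and nothing planned is dropped.
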